7.2 Purpose

The purpose of this study is to characterize the performance and safety of the OPTRELL™ catheter prior to CE-mark registration.

8. Study Design and Endpoints

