20.1 Levels of Significance

All data will be summarized by descriptive analyses. No formal statistical inference is planned. All confidence intervals will use the two-sided 95% confidence level unless otherwise stated.

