20.2 Sample Size Justification

A sample size of 30 subjects will allow characterization of the performance and safety of the OPTRELL™ catheter. Approximately 20 atrial and 10 ventricular procedures will be performed.

The sample size of 30 patients was selected based on previous experience with similar design in first in human assessments of multi-electrode mapping catheters. This study is meant to characterize the catheter's ability to perform safely in various types of arrhythmias. No clinical claims of effectiveness or patient outcomes will be made from this study.

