20.4 Analyses to be conducted

20.4.1 General Conventions

Standard descriptive summaries for continuous data include the number of observations with data, mean, standard deviation (SD), median, minimum, and maximum values. The mean and median will be rounded to one decimal place greater than in the raw data where applicable; the standard deviation will be rounded to two decimal places greater than in the raw data where applicable. In cases where this is not applicable (e.g., average time spent), the mean will be rounded to one decimal place; the standard deviation to two decimal places; the minimum

and maximum to the nearest whole number. These will be referred to as “continuous summaries”.

For categorical data, the count and percent will be provided. Percentages will be based on the number of subjects without missing data. For adverse event and device effects data, percentages will be based on the number of subjects in the analysis population being used in the analysis. When count data are presented, the percentage for zero counts will be suppressed in order to draw attention to the non-zero counts. Frequency counts will be presented as whole numbers and percentages will be rounded to one decimal place. This will be referred to as “categorical summaries”.

Adverse Events (AE) tables will be sorted by decreasing frequency of events, unless otherwise specified.

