20.4.7 Analysis for Primary Endpoints

Primary Effectiveness Endpoint is defined as the completion of all pre-ablation mapping requirements and any clinically indicated mapping with the OPTRELL™ catheter without resort to non-study mapping catheter(s).

The primary effectiveness endpoint (success/failure) will be summarized using categorical summaries for the PP Analysis Set.

The number of subjects who started the pre-ablation mapping procedures with the OPTRELL™ catheter will be summarized overall, per chamber and by arrhythmia subgroup. The proportion of subjects who meet the requirements for success in the primary effectiveness endpoint will be summarized per chamber and overall.

A listing of the primary effectiveness endpoint will be provided.

Primary Safety Endpoint is defined as the incidence of serious adverse events related to the OPTRELL™ catheter within 7 days of index procedure. An SAE will be counted as related to the OPTRELL™ catheter if the relationship to a study catheter is anything other than 'Not Related'.

The number of subjects with SAEs related to the study catheter will be summarized in the Safety Analysis Set overall, by chamber and by each arrhythmia subgroup by Preferred Term and level of relationship. All tables will present summaries both by subject and by event.

If a subject has multiple occurrences of an event within a level of summarization, then for the by-subject summaries only a single occurrence will be counted at each level of summarization at the highest level of severity/relationship; for the by-event summary each event will be counted.

Device related SAEs will be defined and summarized similarly. All SAEs will be listed by System Organ Class and Preferred Term, severity, causality (defined as possible, probable or having a causal relationship to the device and/or procedure), anticipation and outcome.

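### Should the plan attach confidence intervals to its two primary endpoints, given that section 20.1 sets a 95% level that section 20.4 never uses?

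*Combined protocol and SAP*

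**What the plan says.** Section 20.1 states that all data are summarised descriptively with no formal inference, and then sets a convention: "All confidence intervals will use the two-sided 95% confidence level unless otherwise stated". Nothing later in section 20 says which quantity receives an interval, or by what method.

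Section 20.4.1 defines the standard table for categorical outcomes: "For categorical data, the count and percent will be provided". For counts of zero, "the percentage for zero counts will be suppressed in order to draw attention to the non-zero counts".

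Section 20.4.7 applies this to both primary endpoints. For effectiveness: "The primary effectiveness endpoint (success/failure) will be summarized using categorical summaries for the PP Analysis Set". For safety: "The number of subjects with SAEs related to the study catheter will be summarized in the Safety Analysis Set overall, by chamber", and also by arrhythmia subgroup, by subject and by event. The same section plans a listing of the effectiveness endpoint and a listing of all serious adverse events with severity, causality, anticipation and outcome.

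On size, section 20.2 says "A sample size of 30 subjects will allow characterization of the performance and safety of the OPTRELL™ catheter" and "Approximately 20 atrial and 10 ventricular procedures will be performed". It gives precedent as the reason for 30 and says no claims of effectiveness or patient outcomes will be made. Section 6.3 repeats this. Section 7.2 gives the aim: "The purpose of this study is to characterize the performance and safety of the OPTRELL™ catheter prior to CE-mark registration".

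**The concern.** A level for intervals that no analysis uses looks like an omission. It suggests that intervals were intended for the primary endpoints and then left out of section 20.4.7. Section 20 calls itself the statistical analysis plan, so no other document is named that would supply them.

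The stake is how the results are read. The study precedes CE-mark registration, and section 20.2 says that 30 subjects will characterise the device without saying how precisely. If no catheter-related serious event occurs, the safety row shows a 0 with neither a percent nor an interval, and that is the result most easily taken as reassurance. The ventricular group, at about 10 subjects, is where the reassurance would be thinnest. Section 6.4.1 says the level of entrapment risk is not yet known, so what the data cannot exclude is a fair question.

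**Working it through.** **Inputs.** Level: two-sided 95% (section 20.1), so 0.025 in each tail. Numbers: 30 in total, about 20 atrial and 10 ventricular (section 20.2), assuming all are analysed. Interval method: none is named, so Clopper-Pearson is assumed and Wilson is used as a check. Event and success rates: none are given, so the outcomes below are illustrations.

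**The plan's own figure.** N = 30 cannot be reproduced or refuted. The documents give no assumed rate, margin, power or precision target, and sections 6.3 and 20.2 rest the number on precedent.

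**Step 1: what the intervals would show.** For 0 events in n, the upper limit is 1 − 0.025^(1/n). For n successes in n, the lower limit is 0.025^(1/n). For other counts x, the limits are the 0.025 quantile of Beta(x, n − x + 1) and the 0.975 quantile of Beta(x + 1, n − x).

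- n = 30: 0.025^(1/30) = 0.884, so 0/30 has upper limit 11.6% and 30/30 has lower limit 88.4%.
- n = 20: 0.025^(1/20) = 0.832, giving 16.8% and 83.2%.
- n = 10: 0.025^(1/10) = 0.6915, giving 30.8% and 69.2%.

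| Result | Percent | Exact 95% limits |
|---|---|---|
| 1/30 | 3.3 | 0.1 to 17.2 |
| 2/30 | 6.7 | 0.8 to 22.1 |
| 1/10 | 10.0 | 0.3 to 44.5 |
| 29/30 | 96.7 | 82.8 to 99.9 |
| 27/30 | 90.0 | 73.5 to 97.9 |
| 9/10 | 90.0 | 55.5 to 99.7 |

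Wilson upper limits are 11.4% for 0/30 and 27.8% for 0/10, so the picture does not depend on the method.

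The chance of seeing no event is (1 − p)^n. If the true rate of related serious events were 10% (an assumption), it is 0.90^30 = 4.2% in 30 subjects and 0.90^10 = 34.9% in 10. At 5% it is 21.5% and 59.9%. The imprecision is therefore real.

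**Step 2: does anything in the plan depend on it?** Section 20.1 plans no inference. Section 6.3 limits the study to description. Neither primary endpoint has a threshold that a limit could pass or fail, so no conclusion the plan is designed to draw would change.

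**Step 3: is information lost?** An exact interval is a function of x and N alone. For effectiveness, x and its percent are tabulated. For safety, x is tabulated and the denominator is the Safety Analysis Set, whose size is reported under section 20.4.3. When x = 0 the count is still printed and only the percent is left out, and 0/30 is 0% in any case. At this size the two listings also let a reader see every failure and every serious event individually.

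**Step 4: would requiring intervals be neutral?** Only if the denominators stay as planned. Section 20.4.1 bases percents on subjects without missing data, with the whole analysis set used for adverse events and device effects, and section 20.4.9 allows no imputation. Suppose, as an assumption, that the per-protocol set has 30 subjects, with 28 successes and 2 missing outcomes. The plan's rule gives 28/28, with lower limit 0.025^(1/28) = 87.7%. Taking the whole set as N gives 28/30 = 93.3% (77.9% to 99.2%), which in effect counts missing as failure. That would be a different analysis, beyond adding an interval.

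**The case for a change.** The best argument for a change is that it costs almost nothing. An exact interval needs no hypothesis, and section 20.1 sets the level in the same paragraph that rules out formal inference. Naming the method, the denominator and the table row in advance stops anyone choosing them after the data are seen. Small ventricular numbers in a new device are also where a bare count misleads most.

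Much of this stands. The level is indeed unassigned, the limits are wide, and printing them would be good practice.

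It does not show a fault in the plan. Choosing the method afterwards leaves little room for harm when exact and Wilson limits differ by 0.2 percentage points for 0/30 and 3.0 for 0/10, and when no decision follows from either. The section 20.1 wording permits intervals, so the absence of an assignment does not prohibit them. The zero-percent rule is table formatting. The limits would themselves be nominal: they treat subjects as independent, although up to 4 sites and selected skilled operators take part. They would also do nothing about who enters the per-protocol set.

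**Conclusion.** No change to the plan is called for. Section 20.1 sets a level that section 20.4 does not use, but following the plan as written still yields sound descriptive results: counts, percents, stated analysis sets and full listings for both primary endpoints. The gap is one that analysts fill sensibly, by adding exact two-sided 95% limits to the by-subject proportions at the reporting stage on the plan's own denominators.

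The precision is limited whether or not it is printed: about 11.6% as the upper limit after 0/30 and 30.8% after 0/10, or 88.4% and 69.2% as the lower limits after complete success. These figures assume that all 30 planned subjects are analysed, that the split is 20 and 10, that subjects are independent and that the method is Clopper-Pearson; smaller sets would widen them.

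The conclusion rests on the study remaining descriptive. If a performance goal or a formal claim were attached to either endpoint, the interval and its method would have to be specified.

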20.4.8 Analyses of Secondary and Additional Endpoints

Secondary Safety Endpoints will be analyzed using the Safety Analysis Set:

- All Serious Adverse Events
- All non-serious Adverse Events related to the OPTRELL™ catheter during the 7-day follow-up period

The number of subjects experiencing adverse events and the number of adverse events will be summarized in the Safety Analysis Set overall, per chamber and by each arrhythmia subgroup using categorical summaries similar to the primary safety endpoint.

A listing of device deficiencies including the category and timing of the device deficiency will also be provided. Each deficiency will indicate whether it resulted in an adverse event.

The below endpoints will be analyzed using the PP Analysis Set:

- Physician feedback on deployment, maneuverability, and signal quality acquired with the OPTRELL™ Catheter for mapping in the atria and ventricles.
A post-procedure survey of 11 questions, each with individual sub-questions will be administered. Each question/sub-question will be answered by the physician using a Likert scale of 1 to 7 (1=poor and 7=excellent) and will be summarized. The summary results of each question will be presented overall, by catheter configuration, per chamber and for each arrhythmia subgroup using continuous summaries. A 12th question will solicit any additional feedback from the physician in a free text field. A by subject listing including all feedback results will be provided.
- Procedural parameters will be analyzed by heart chamber, by catheter configuration and by arrhythmia subgroup.
 - Pre-ablation mapping duration with the OPTRELL™ catheter (i.e. time between first and last mapping point prior to first ablation point, as measured on CARTO®) and total procedure time, will be analyzed using continuous summaries of subjects where mapping with the study device is initiated.
 - Mapping density adequacy with the OPTRELL™ catheter (as assessed by investigator) will be presented with categorical summaries.
 - Mapping algorithms used with the OPTRELL™ catheter (i.e. voltage map and/or LAT.) will be presented with categorical summaries.
 - CARTO® 3 modules used with the OPTRELL™ catheter will be presented with categorical summaries.
 - Types of areas of interest captured with the OPTRELL™ catheter (e.g. PV triggers, previous PVI lesion gaps, non-PV AF Foci, ventricular scar slow conduction zone, left atrial flutter critical isthmus, cavo-tricuspid isthmus, etc.) in pre-ablation mapping (as indicated by the investigator) will be summarized using categorical summaries.

For each of the above procedural parameters, the denominator will be the number of subjects where mapping with the study device is initiated.
Listings will be provided.

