6.1 Background Information

Complex tachycardias are often the result of scarring in the atrial and ventricular cardiac tissue - from myocardial infarction, cardiomyopathies, previous ablation, or surgical incisions. These conditions result in necrotic and fibrotic tissue being interspersed with areas of surviving tissue, allowing for slow pathways and re-entrant circuits to form. Variable morphology and cycle lengths of these arrhythmias make it difficult to identify reentry circuits and conduction channels.

The OPTRELL™ catheter is a multielectrode ECG mapping catheter that works in conjunction with the CARTO® 3 EP Navigation System. It is designed for deployment in a heart chamber through an 8.5 F guiding sheath. This bi-directional deflectable catheter consists of six 2 F spines that are parallel to each other on its deflectable tip, each spine having eight platinum electrodes that are used for stimulating and recording. The product is intended to improve the resolution and clarity of electrical signal mapping for electrophysiology procedures.

Multielectrode mapping (MEM) is the process by which physicians can quickly capture activation maps, namely electrical function over a wide area of the atrial or ventricular chamber with just “one click” or movement of the catheter. Based on the MEM information acquired, physicians can then locate the earliest point of a re-entrant circuit or slow pathway for many complex arrhythmias while better defining the channels to ablate.

In a clinical setting, the identification of the foci by this network of electrodes could permit rapid identification of target sites and allow for reduced mapping and/or procedure time.

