6.4.3 Known Potential Benefits

For ischemic and non-ischemic VT, more electrophysiologists are performing mapping while the patient is in VT, which can frequently be hemodynamically unstable and necessitates rapid mapping tools. High-density mapping catheters are becoming critical for this workflow and drive overall VT procedural efficiency. The “grid” design of the OPTRELL™ catheter is expected to contribute to the improvement of workflow and procedural efficiency by:

- Availability of a non-arrhythmogenic high density diagnostic catheter that maneuvers well in varied ventricular anatomy (including trabeculation and papillary muscles) and is readily and consistently visualized, without compromising workflow efficiency.
- High-resolution signals to identify electrical activity in low voltage area / scar / border zones.
- Greater mapping density and / or mapping efficiency, particularly when mapping while the patient is in hemodynamically unstable VT.

For complex atrial arrhythmias, electrophysiologists are looking for high density maps to identify triggers, activation, and mechanism. The OPTRELL™ catheter is expected to contribute to improving mapping for complex atrial arrhythmia by:

- Ultra high density mapping catheter to allow for quick and high density capture of arrhythmias.
- Fixed spacing of splines/electrodes to allow for understanding of conduction wavefront propagation.
- Ultra high density mapping catheter to allow for detailed mapping of complex circuits and mechanisms.
- Catheter form factor that minimizes ectopic beats.

The potential effectiveness and efficiency gains stated above are expected to provide benefit to patients by shorter procedure times and better clinical outcomes.

7. Objectives and Purpose

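### Should 20.4.8 split pre-ablation mapping duration by map completion and give mapping density a numeric definition?

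*Combined protocol and SAP*

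**What the plan says.** Section 20.4.8 names the parameter "Pre-ablation mapping duration with the OPTRELL™ catheter (i.e. time between first and last mapping point prior to first ablation point", measured on CARTO. Together with total procedure time it "will be analyzed using continuous summaries of subjects where mapping with the study device is initiated". The planned breakdowns of procedural parameters are heart chamber, catheter configuration and arrhythmia subgroup. Section 20.4.6 adds a presentation by chamber mapped.

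On density, sections 5, 8.2.3 and 14.2.4 list the term alone, with no unit or formula. Section 20.4.8 analyses "Mapping density adequacy with the OPTRELL™ catheter", with the rule "as assessed by investigator) will be presented with categorical summaries". Adequacy of density is also the fourth completion requirement in 14.2.2 and the fourth Y/N element in 20.4.6.

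On areas of interest, 14.2.4 collects both kinds and counts. Section 20.4.8 covers "Types of areas of interest captured with the OPTRELL™ catheter" only, as does section 5. The matching line in 8.2.3 has a word missing.

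Section 20.4.8 closes its procedural parameters with "Listings will be provided".

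**The concern.** Section 6.1 says that finding foci with the electrode network "could permit rapid identification of target sites and allow for reduced mapping and/or procedure time", so a short duration invites a favourable reading. A map abandoned early also gives a short duration, and the summary does not separate the two cases. The definition in brackets does not say what happens if another catheter contributes points before ablation.

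Section 6.4.3 lists "Greater mapping density and / or mapping efficiency" among the expected benefits in ventricular tachycardia. That is a matter of degree, which a yes/no judgement of adequacy cannot describe. Because the judgement is also a requirement for effectiveness success, the density row seems to repeat the primary endpoint. Counts of areas of interest are collected and then not tabulated.

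At stake is whether these additional endpoints can be read as a description of how the catheter performs.

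**Working it through.** The only planning figure is the sample size of 30 (about 20 atrial and 10 ventricular, section 20.2). It rests on earlier experience, with no alpha, power, rate or SD, so there is nothing to reproduce. The point does not depend on it except as a denominator.

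**Can uncompleted maps enter the duration summary?** Yes. The PP set in 20.3 needs eligibility and started mapping, not completion. Section 20.4.7 scores success or failure in that same set. No section splits duration by completion.

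**What could pooling do?** Let k of n subjects have uncompleted maps. Let m be the mean duration of completed maps and r·m that of uncompleted ones. Then

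pooled mean = [(n − k)m + k·r·m]/n = m[1 + (k/n)(r − 1)],

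so the relative difference from the completed-map mean is (k/n)(r − 1). Here n comes from 20.2; k and r are assumed, because the documents give neither.

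| k | n | r = 0.2 | r = 1 | r = 2 |
|---|---|---|---|---|
| 0 | any | 0 | 0 | 0 |
| 1 | 30 | (1/30)(−0.8) = −2.7% | 0 | (1/30)(1) = +3.3% |
| 1 | 10 | (1/10)(−0.8) = −8.0% | 0 | (1/10)(1) = +10.0% |

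The sign depends on r: an early switch shortens the mean, a difficult map lengthens it. The table compares two summaries of different populations. It is not an estimate of bias in the planned one.

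**What else will the reader see?** Section 20.4.1 requires median, minimum and maximum beside the mean, so one extreme duration shows in the range while the median is less affected. Section 20.4.6 presents the four completion elements, 20.4.7 promises a listing of the primary effectiveness endpoint, and 20.4.8 promises listings of the procedural parameters. With about 30 rows, duration can be matched to completion subject by subject.

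**Whose points count?** The parameter's name already limits it to the OPTRELL catheter. An analyst who meets points from another catheter has the answer in the name.

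**How far does density overlap the primary endpoint?** Success needs all applicable requirements, including adequate density. With s successes among n subjects, the adequate percentage lies between s/n and 100%. This assumes that the item applies to everyone and that 20.4.6 and 20.4.8 use the same field.

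- 30/30 successes: 100.0% necessarily.
- Assumed 27/30: 27/30 = 90.0% up to 100.0%, with room to differ in 30 − 27 = 3 subjects.

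The same bound holds for any required component of any composite endpoint. Section 20.4.6 presents these items as elements of mapping success, so this is ordinary component reporting. The 20.4.8 row also adds a breakdown by catheter configuration, which 20.4.6 and 20.4.7 do not give.

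**Was a numeric density dropped?** Nothing shows that one was intended. Every other place that puts density to use (section 5, 14.2.2, 20.4.6) relies on investigator-assessed adequacy, and section 20, which declares itself the SAP, does the same. Section 6.4.3 states expected benefits; it does not define an endpoint.

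**Areas of interest.** Sections 5 and 20.4.8 agree on types. The counts in 14.2.4 are a collected field without a table, and 8.2.3 has lost a word.

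**The case for a change.** The best case for a change is that in a descriptive study the summaries are the result, so each should be readable by itself. The plan does not promise to show duration and completion side by side, and a listing is not a defined summary. The ventricular group is small enough for one stopped map to matter. A split table and a few wording edits would cost little and need no new patient data. CARTO copies go to the sponsor anyway, so a numeric density might be obtainable.

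The textual facts stand: there is no split, the density label is undefined in three places, and the counts are not tabulated. The step from there to a defect does not. The split would be a further stratum on a population that is already clearly stated, and it is empty if no map fails. The cells would be very small otherwise, and a listing serves a handful of cases better. A numeric density would be a new endpoint, and the documents do not say what the CARTO copies contain. A favourable reading of short times has little to attach to: there is no comparator and no target time, section 20.1 plans no inference, and sections 6.3 and 20.2 rule out claims of effectiveness or patient outcomes.

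**Conclusion.** No change to the plan follows. The duration point is a gap that an analyst fills sensibly by reading the planned listings beside the completion items. Its effect is zero when all maps are completed and otherwise of unknown sign; the illustrated range for one uncompleted map is −2.7% to +3.3% at n = 30 and −8.0% to +10.0% at n = 10, on assumed durations. The density overlap is normal reporting of a component, and section 20 settles what is analysed. The bare density label, the untabulated counts and the missing word in 8.2.3 are clerical; they alter no result if section 20 is followed as written.

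This rests on three conditions: the study stays descriptive with no claim attached to mapping time or density, the promised listings are produced, and the number of subjects stays near 30. If a later document compared mapping time or density with another catheter, the question would need a fresh look there.
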